#### **11.4.2.1 Adverse events**

The definitions in [Section 10.6.1](#) will be used for AEs. Pre-treatment AEs will be listed and presented separately from treatment-emergent AEs.

Adverse events will be coded according to the most recent version of the Medical Dictionary for Regulatory Activities (MedDRA). Adverse event incidence tables will be presented by MedDRA system organ class (SOC) (sorted by internationally agreed order) and preferred term (PT) sorted in decreasing number of patients within SOCs and further alphabetical order within the same number of patients over different PTs for each age group, the number (n) and percentage (%) of patients experiencing an AE. Multiple occurrences of the same event in the same patient will be counted only once in the tables within a treatment period. The denominator for computation of percentages is the safety population for the entire study and each age group cohort.

Adverse events will be classified into pre-defined standard categories according to chronological criteria:

- Pre-treatment AEs: AEs that occurred or worsened during the pre-treatment period;
- Treatment-emergent AEs (TEAEs): AEs that occurred or worsened during the on-treatment period);
- Post-treatment AEs: AEs that occurred or worsened during the post-treatment period.

If the start date of an AE is incomplete or missing, then the AE will be considered as a TEAE unless a partial date shows it as a pre- or post-treatment event.

All AEs reported in the study will be listed, sorted by patient, and onset date.

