1.5 MODIFICATIONS FROM THE STATISTICAL SECTION OF THE PROTOCOL

In the section of statistical considerations of the protocol, the baseline for white blood cell count, platelet count, and hemoglobin was defined as the mean of 2 samples collected greater than 24 hours apart during the screening period. The baseline definition is modified in the SAP as the average of all measurements taken before the first infusion.

The statistical considerations of the protocol mentions that Infusion Associated Reactions (IAR), Acute phase reaction (APR) and cytokine release syndrome (CRS) will be listed as part of adverse events of special interest (AESI). However, per protocol, AESIs are reported as original signs and symptoms and only IARs were specifically identified in the eCRF. Consequently, APR and CRS cannot specifically be listed, but the details of these AESIs will be provided in patient narratives, and discussed in the clinical study report (CSR) as necessary.

In the section of statistical considerations of the protocol, the post-treatment period was defined as the time after the EOS visit. However, no data are expected to be collected after the EOS visit. Therefore, the post-treatment period has been removed from this SAP.

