2.6.1 Adverse events

2.6.1.1 Definitions

AEs are defined in protocol Section 10.6.1. AEs will be coded according to the version of Medical Dictionary for Regulatory Activities (MedDRA) in use at the time of database lock. Adverse event summaries will include the number of events (N), number (n) and percentage (%) of patients experiencing an adverse event. The denominator for computation of percentages is the safety population for the entire study and for each age group cohort. Sorting order will follow the

internationally agreed MedDRA system organ class (SOC) order, then by decreasing number of patients overall in preferred terms (PTs) within SOCs, and further alphabetically within the same number of patients over different PTs. When more than one PT has same number of events within the same SOC, the order of presentation will be alphabetical in PTs.

The AEs will be classified into different periods of occurrence as follows:

- Pre-treatment adverse events: AEs that started before the start of the first infusion.
- TEAEs: AEs that started during the on-treatment period.

If an AE date/time of onset is incomplete, an imputation algorithm will be used to classify the adverse event within the appropriate adverse event period. The algorithm for imputing date/time of onset will be conservative and will classify an adverse event as treatment emergent unless there is definitive information to determine otherwise. Details on classification of AEs with missing or partial onset dates are provided in [Section 2.11.2](#). If an AE worsens in severity, only the worst severity is captured on the AE log page in the e-CRF.

The AE log page in the e-CRF captures the date when the event became serious. If and when this date is non-missing, it indicates that the AE started as non-serious and became serious after few days. To account for non-serious and serious parts of the AE collected in one AE log page, this AE will be split into two AEs – one non-serious, and one serious AE – with the same AE number, with the following modifications in data for these two AEs:

- Non-serious AE: AE end date, AE outcome, date of death or hospitalization, autopsy information, criterion for serious adverse event (SAE) will be blank.
- Serious AE: AE start date will use the date the event became serious.

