Action taken towards study drug and action taken (toward AE) will be considered in relation to the date the event became serious, the last infusion date and dosing information, and a determination will be made, in consultation with safety monitor of the trial, as to whether the recorded fields belong to non-serious AE or serious AE; then the decision will be implemented in analysis. Any such decision will be rationalized in the CSR.

The primary focus of adverse event reporting will be on treatment-emergent adverse events. Pre-treatment adverse events will be listed separately.

Start day of a pre-treatment AE = Start date of AE – first infusion date.

Start day of treatment emergent AE relative to first infusion = Start date of AE – first infusion date + 1.

Start day of treatment emergent AE relative to last infusion = Start date of AE – last infusion date + 1.

2.6.1.2 *Treatment-emergent adverse events*

An overview of TEAEs will be provided by age group cohorts and overall to include (potentially related is defined as either 'related' or 'possibly related' as assessed by the investigator):

- TEAEs.
- TEAEs potentially related to study treatment.
- TEAEs by the worst severity.
- TEAEs leading to treatment discontinuation.
- TEAEs leading to study withdrawal.
- TEAEs leading to dose reduction.
- TEAEs leading to study treatment interruption.
- Protocol-defined IARs.
- Algorithm-defined IARs.
- Treatment-emergent serious adverse events.
- Treatment-emergent serious adverse events potentially related to study treatment.
- TEAEs with fatal outcome (Deaths).
- Treatment-emergent pregnancies.
- TEAEs which are considered symptomatic overdose.
- Dose-limiting toxicities (collected in the adverse event log page in e-CRF, see protocol Section 8.3.4.2.1 for details).

The following summaries will be produced by primary SOC and PT, by age group cohorts and overall:

- TEAEs.
- TEAEs by the worst severity (ie, mild, moderate, or severe).
- TEAEs potentially related to study treatment.

The most common TEAEs are defined as those with percentage of events $\geq 2\%$ and number of patients ≥ 2 in all age cohorts combined. The most common TEAEs by SOC and PT will be provided in descending order of overall incidence by age group cohorts and overall.

TEAEs by the latest infusion dose immediately preceding the start of AE will be provided by SOC and PT, by age group cohorts and overall.

2.6.1.3 *Adverse events of special interest*

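### The SAP drops worsening from the protocol's TEAE definition without declaring it, so some non-serious screening-onset AEs that worsen after dosing are left out of the TEAE tables

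*SAP*

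**What the plan says.** Protocol 11.4.2.1 gives the definition as "Treatment-emergent AEs (TEAEs): AEs that occurred or worsened during the on-treatment period". SAP 2.6.1.1 gives it as "TEAEs: AEs that started during the on-treatment period", and classes any AE with onset before the first infusion as pre-treatment, whatever its later course. On reporting, the SAP adds: "Pre-treatment adverse events will be listed separately".

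SAP 2.6.1.1 also describes what the log holds: "If an AE worsens in severity, only the worst severity is captured on the AE log page in the e-CRF". The one change over time that receives a new date is a move from non-serious to serious, where the record is split: "Serious AE: AE start date will use the date the event became serious".

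SAP 1.5 names three departures from the protocol's statistical section: the hematology baseline, the listing of acute phase reactions and cytokine release syndrome, and the observation periods ("Therefore, the post-treatment period has been removed from this SAP"). The TEAE definition is not among them.

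**The concern.** AEs and TEAEs are part of the primary endpoint (Protocol 9.1), and SAP 2.6.1.1 makes TEAEs the main focus of AE reporting. The definition feeds the overview, the SOC and preferred-term tables, worst severity, relatedness, dose reduction and interruption, and the by-dose table (SAP 2.6.1.2). It also feeds the infection and bleeding analyses, which are defined on TEAEs (SAP 2.6.1.4).

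AEs are collected from consent (Protocol 10.6.2) and screening can last up to 60 days (Protocol 6.2.1). An event can therefore begin before dosing and become worse after an infusion. The protocol counts that event and the SAP does not. Its post-dose severity would then sit on a record labelled pre-treatment. The SAP also declares another change to the period definitions while staying silent on this one, so a reader comparing the two documents would not know that the definition had narrowed.

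**Working it through.** The plan gives no figure to reproduce. The check is to classify the same event under both texts.

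Inputs: the TEAE definitions (Protocol 11.4.2.1, SAP 2.6.1.1); the single-record and seriousness-split rules (SAP 2.6.1.1); the missing-date rule (SAP 2.11.2); AE collection from consent (Protocol 10.6.2); minimum enrolment of 20 (Protocol 11.1).

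Take an AE with onset in screening that goes from mild to severe after the first infusion.

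| Case | Protocol | SAP |
|---|---|---|
| Known onset, stays non-serious, one log record | TEAE | Pre-treatment, listed only |
| Becomes serious after dosing | TEAE | Serious part is a TEAE through the split |
| Worsening has its own record with a post-dose start | TEAE | TEAE |
| Onset date incomplete, pre-dose onset cannot be confirmed | TEAE | TEAE by the missing-date rule |

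Only the first row differs. The split does not recover that event because it never becomes serious. The missing-date rule does not recover it because its start date is known. With all other rules held the same, the SAP's set of TEAEs is contained in the protocol's set, so the difference runs in one direction: too few.

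The log alone cannot repair this. It holds the worst severity, and the SAP describes no date for a severity increase. An event that peaked before dosing and one that peaked after it can look the same.

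The by-dose table has the same difficulty: "TEAEs by the latest infusion dose immediately preceding the start of AE will be provided by SOC and PT". An AE that began before the first infusion has no preceding dose, so restoring the wording without a worsening date would leave that table undefined for these events.

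Scale. If k affected patients have no other TEAE in a row, the row falls by k/n. With k = 1 and n = 20, that is 1/20 = 5 percentage points. A patient who already has a TEAE in the row changes nothing in its patient count. One display depends on a small count: "The most common TEAEs are defined as those with percentage of events" of at least 2%, together with at least 2 patients. A term that meets the percentage condition and has exactly 2 patients, one of them only by worsening, falls to 2 − 1 = 1 patient and leaves that table.

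**The case against.** The strongest reply is that little is lost. The event must start within a short screening window, have a known date, be ongoing at first infusion, worsen later, stay non-serious and have no separate record. Much of what could matter is also reported elsewhere:

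- Symptoms of infusion-associated reactions are recorded separately (Protocol 10.6.2), and clinically significant laboratory worsening from screening is to be documented as an AE (Protocol 9.1.8).
- Related events may appear in the protocol-defined infusion-reaction summaries, whose SAP definition has no start-time condition (SAP 2.6.1.3). This is not certain, because SAP 2.6.1.2 also places those reactions inside an overview of TEAEs.
- Laboratory, vital-sign and ECG abnormality tables and the examination shift tables (SAP 2.6.2, 2.6.3, 2.6.5 to 2.6.7) do not use the AE start date. Nor do the dose-limiting-toxicity row and listing (SAP 2.6.1.2, 2.6.1.8) or the narratives for liver criteria and permanent discontinuation (SAP 2.10).

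All of this stands, and it limits the weight of the point. It does not remove the mismatch: the TEAE tables would still not follow the protocol definition, and the departure is undeclared. What remains without summary-level cover is mainly non-serious symptomatic worsening judged unrelated.

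A reader might infer more, and three such inferences fail. First, that TEAE incidence is materially understated: the documents give no number of affected events, and k/n arithmetic shows only the size of the denominator. Second, that dose escalation, stopping or the monitoring committee's review is compromised: these act on AE data directly (Protocol 6.3, 8.3.4.1, 8.3.4.2), not on the SAP's TEAE flag. Third, that SAP 2.11.2 already resolves doubtful cases as TEAEs: it deals with missing start dates and times, not with missing dates of worsening.

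**Conclusion.** The SAP as written departs from the protocol's TEAE definition without declaring it, and none of its other rules closes the gap for a known screening-onset AE that worsens after dosing, stays non-serious and sits on one record. TEAE counts can only be too low by comparison. The number of such events is unknown and probably small. The figure of 5 points per patient assumes 20 patients and no other TEAE for that patient in the row; it is not an expected bias. The effect is confined to the reported safety tables. The conclusion rests on the SAP's description of the AE log, which mentions no date of severity increase. The point should be corrected because the definition serves the primary endpoint and the correction is cheap.

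**What to change.** In SAP 2.6.1.1, define a TEAE as an AE that started, or worsened in severity, on or after the first infusion. Query AEs ongoing at first infusion for the date of any severity increase, and use that date as the onset of the worsened part, including in the by-dose table.

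State a new rule for cases where the timing cannot be resolved, for example to flag them and show TEAE counts with and without them. This would extend SAP 2.11.2; it is not already there. Leave the serious/non-serious split unchanged, since nothing here shows it to be wrong.

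If the sponsor prefers the onset-only definition, declare and justify it in SAP 1.5.

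The cost is SAP wording, one derivation, a second set of counts if there are unresolved cases, and a few retrospective queries. TEAE counts may rise slightly.

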The following are AEs of special interest:

Protocol-defined IAR: Any AE that is considered related or possibly related to study treatment as judged by the investigator or the sponsor is defined as a protocol-defined IAR. Sponsor identification will reconcile with investigator identification of IAR before the database lock.

The following summaries will be produced by primary SOC and PT, by age group cohorts and overall:

- Protocol-defined IARs.
- Protocol-defined IARs by the worst severity.
- Protocol-defined IARs started during infusion.
- Protocol-defined IARs started between 0 hours (exclusive) and 3 hours (exclusive) post end of infusion.
- Protocol-defined IARs started between 3 hours (inclusive) and 24 hours (inclusive) post end of infusion.
- Protocol-defined IARs started between 24 hours (exclusive) and 72 hours (inclusive) post end of infusion.
- Protocol-defined IARs started after 72 hours post end of infusion.

Algorithm-defined IAR: All AEs that start between the start of infusion and the end of infusion plus 24 hours are defined as algorithm-defined IARs, irrespective of the perceived relation with study treatment.

The following summaries will be produced by primary SOC and PT, by age group cohorts and overall:

- Algorithm-defined IARs (including any TEAEs with missing time but happened on the same day or the day after the infusion)

A subset of protocol-defined IARs will also be defined programmatically by searching for preferred terms within Hypersensitivity SMQs (identified using SMQ code 20000214 Broad and Narrow scope). The summaries of Hypersensitivity IARs will be provided by primary SOC and PT.

Pregnancy: Pregnancy of a female patient entered in the study as well as pregnancy occurring in female partner of a male patient enrolled in this study is captured as an adverse event. In addition, e-CRF provides urine pregnancy test results as positive or negative. Labs provide serum pregnancy test results. Pregnancies will be provided in the overview of AE summary and the pregnancy test results will be provided as part of patient narrative.

Symptomatic overdose: This is captured as an adverse event in this study. For details, please see Section 10.6.4.1 in the protocol. The symptomatic overdose data will be provided as part of patient narrative.

Asymptomatic overdose: This is captured as an adverse event with verbatim term as 'Asymptomatic overdose'. Asymptomatic overdose data will be provided as part of patient narrative.

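### An AE that becomes serious is split into two records and the second is re-dated, so it adds one to the event count N and can enter a second, later IAR onset window

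*SAP*

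**What the plan says.** SAP 2.6.1.1 acts on the e-CRF field holding the date an event became serious. When that field is filled, "it indicates that the AE started as non-serious and became serious after few days", and "this AE will be split into two AEs – one non-serious, and one serious AE – with the same AE number". The second record is re-dated: "Serious AE: AE start date will use the date the event became serious". The first loses some fields: "Non-serious AE: AE end date, AE outcome, date of death or hospitalization, autopsy information, criterion for serious adverse event (SAE) will be blank". Its start date is not among the fields changed. Relatedness and severity are not listed as changed on either record.

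On severity, the same section notes that "If an AE worsens in severity, only the worst severity is captured on the AE log page in the e-CRF". On counting, it says "Adverse event summaries will include the number of events (N), number (n) and percentage (%) of patients experiencing an adverse event".

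Three sets of tables depend on when an AE started:

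- SAP 2.6.1.3 tabulates protocol-defined IARs in five windows: during infusion, then 0–3, 3–24, 24–72 and over 72 hours after the end of infusion. Its definition of a protocol-defined IAR rests on relatedness alone, with no time limit.
- The same section defines a second class by timing: "All AEs that start between the start of infusion and the end of infusion plus 24 hours are defined as algorithm-defined IARs".
- SAP 2.6.1.2 attributes events to dose: "TEAEs by the latest infusion dose immediately preceding the start of AE will be provided by SOC and PT".

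The SAP provides a case-by-case decision on split events only for the action-taken fields (end of 2.6.1.1). No text collapses the two records by AE number for N, or restores the first onset for the window and dose tables.

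**The concern.** The split suits an SAE table but not tables of event counts, onset timing or dose. There, one clinical event enters as two, and the second has a start date at which nothing new began; only its regulatory status changed.

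Safety is the primary objective (Protocol 5.1), and onset time helps to tell reaction types apart. Protocol 10.6.1.3.2.1 places hypersensitivity early in or shortly after the infusion. Protocol 10.6.1.3.2.2 places acute phase reactions typically at 12 to 72 hours. SAP 1.5 states that acute phase reactions and cytokine release syndrome cannot be listed separately, so the window tables are the main tabular evidence on timing. An early reaction re-dated into the 24–72 hour window takes on the timing of an acute phase reaction. With about 20 patients, one or two such records can be visible in a table of serious or severe events.

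**Working it through.** The plan states no figure to reproduce, so the check traces the rules on example records.

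**Event count.** With M events, of which k convert, N becomes M + k, an inflation of k/M. The documents give neither number. On assumed values:

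- M = 50, k = 1: N = 51, +2.0%
- M = 100, k = 3: N = 103, +3.0%
- M = 200, k = 2: N = 202, +1.0%

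The log holds one severity grade, the worst, and the split does not change it. Both records carry it, so the event count in that severity row also rises by k.

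**Onset windows.** Time h is in hours after the end of infusion, and the delay to seriousness is assumed. The window is that of h for the non-serious record and of h + delay for the serious one.

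| Onset h | Non-serious record | Serious 24 h later | 48 h later | 72 h later | 120 h later |
|---|---|---|---|---|---|
| −1 | during | 3–24 | 24–72 | 24–72 | >72 |
| 1 | 0–3 | 24–72 | 24–72 | >72 | >72 |
| 12 | 3–24 | 24–72 | 24–72 | >72 | >72 |
| 30 | 24–72 | 24–72 | >72 | >72 | >72 |
| 60 | 24–72 | >72 | >72 | >72 | >72 |
| 80 | >72 | >72 | >72 | >72 | >72 |

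The first three rows generalise. Infusions last up to about 4.5 hours (Protocol 8.3.2), so an onset during infusion lies between −4.5 and 0. Adding 24 gives 19.5 to 24, which is the 3–24 window. An onset between 0 and 3 moves to 24–27, and one between 3 and 24 moves to 27–48; both fall in the 24–72 window. So an onset during infusion or within 24 hours after it always gains a second window once the delay reaches 24 hours. Later onsets may not: 30 h with a 24 h delay stays put, as does any onset already beyond 72 h.

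**Date against hours.** The SAP describes only a date for becoming serious. An event dated serious on the calendar day after onset could have become so anywhere from just over 0 to just under 48 hours later. The serious record may therefore not be assignable to an hour-based window at all.

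**Algorithm-defined IAR status.** The non-serious record keeps its start and so its status. The serious record may lose or keep it. SAP 2.6.1.3 retains events without a time on the infusion day or the day after, and SAP 2.11.2 defaults ambiguous timing to algorithm-defined IAR. Where it is kept, that table's N is also raised by one.

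**Dose.** Infusions are scheduled at 14-day steps from Day 1, each ±3 days (Protocol 8.3.2). Consecutive infusions are therefore at least 14 − 3 − 3 = 8 and at most 14 + 3 + 3 = 20 days apart. A second dose arises only if the event became serious on or after the next infusion and the dose level had changed. That is compatible with the protocol, because 8.3.4.1 lets an infusion go ahead with an unresolved AE, but it is a narrow case.

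**Patient counts.** Protocol 11.4.2.1 counts repeat occurrences in one patient once, so n and % for a term within one table do not move. The patient can appear in two window tables.

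**The case against.** The strongest reply is that the rule is pre-specified, hides nothing and affects few records. Both halves share an AE number, all AEs are listed (Protocol 11.4.2.1), and every SAE and protocol-defined IAR has a narrative (SAP 2.10). In an open-label, descriptive study of about 20 patients, any split event can be traced. The split also does useful work. The SAP defines TEAEs by when they started, so a separate serious date lets a pre-treatment AE that becomes serious on treatment count as a treatment-emergent SAE. All of this stands. It limits the harm and argues for keeping the became-serious date, but it does not make N or the window tables correct.

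A reader might infer more than the documents support:

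- **That most serious IARs are affected, or the serious reactions as a class.** Reactions serious from onset are never split, and no figure is given for the share that convert.
- **That seriousness through prolonged hospitalization usually dates from after the 24-hour stay in Protocol 10.3.1.** Neither document says how that date is set. A prolongation decided at 24 hours would be dated the day after infusion.
- **That a reaction drops out of the IAR tables or out of its true window.** The non-serious record stays in both; the split adds a record and removes none.
- **That a whole reaction is the unit doubled.** Protocol 10.6.2 requires IAR symptoms to be recorded separately. Only a symptom record with its own became-serious date is split, though several such symptoms would give several duplicates.

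**Conclusion.** The point holds in a limited form. Followed as written, SAP 2.6.1.1 gives an event count that is one too high for each converted AE, overall and in its worst-severity row. It also gives a false later onset for converted reactions that began during infusion or within 24 hours after it and became serious at least 24 hours later. Attribution to a second dose is possible but rare.

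This rests on two readings: that relatedness and severity carry over to both records because they are not listed as changed, and that N counts records because no other unit is named. The number affected is unknown and may be small. The change is still worth making before database lock, because the rule produces a wrong result in tables that serve the primary objective.

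**What to change.** Add to SAP 2.6.1.1:

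- The number of events counts distinct AE numbers.
- IAR status, onset-window tables and dose attribution use the original onset date and time, with seriousness carried as a flag on the one event.
- The became-serious date is used for SAE tables, listings and narratives, and to classify a pre-treatment AE that becomes serious on treatment as a treatment-emergent SAE.

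This takes a few lines of text and no new data, since the shared AE number already links the records. The small cost is that the AE dataset must hold two onset variables, with each table's specification naming the one it uses.
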